10.3 Storage for future studies

In addition to these investigations, all patients will be asked for informed consent to store biological material for future studies. Material for future investigations will be shipped to the central laboratory of the Academic Medical Center Amsterdam and/or Copenhagen University Hospital. More details can be found in the study lab manual. All materials are anonymized and stored for a maximum of 15 years after end of study, after which the samples will be destroyed.

10.4 Response evaluation

Response will be evaluated without CT (clinical response) at cycle 3, 9, and 12, after cycle 15 every 3 months for 2 years, and every 4 months for the 3rd year (until 51 months), and month 51. Response will be evaluated with CT at cycle 15 and month 27, and in case of suspected progressive disease. Response will be determined according to the definitions of response in the IWCLL updated NCI-WG guidelines [Hallek et al., 2008]. For a tabular summary of all criteria of response definition in CLL patients see Appendix B.

10.5 Quality of Life assessment

Health related outcome parameters will be collected in this study, i.e. quality of life (QoL).

QoL will be assessed at entry, after 15 induction cycles and at 6 months, 1, 2 and 3 years after start maintenance/ observation.

The quality of life measurements will be continued after the patient is off protocol treatment, but discontinued when progression has been observed.

- EORTC QLQ-C30 questionnaire
- EORTC QLQ-CLL16

Collection of the QoL questionnaires will be performed in the following manner:

A QoL coordinator will be assigned in each participating center. The QoL questionnaire collection is left to the responsibility of the QoL coordinator. As soon as a patient is registered at the HOVON Data Center (HDC) the QoL coordinator is notified by email. Patient study number, (partial) date of birth and date of registration are mentioned in this mail.

The patient will be provided a paper print out of the questionnaire.

The baseline questionnaire will be handed or sent to the patient by the QoL coordinator. At the time points mentioned in the beginning of this section, the coordinator will hand over the questionnaire at the correct date.

The QoL coordinator will collect the questionnaire from the patient and will send them to the HOVON Data Center.

The questionnaires are described in appendix L.

10.6 Minimal Residual Disease

Minimal residual disease (MRD) levels will be examined by quantitative highly sensitive flow cytometry (MRD flow) in the peripheral blood and in the bone marrow at:

- The Department of Hematology, Rigshospitalet, Copenhagen University Hospital for the Nordic sites
- The Academic Medical Center, Amsterdam laboratory of Hematology for the HOVON sites

MRD will be quantified by six-color flow cytometry with a sensitivity of at least 10^{-4} as previously validated against ASO-primer realtime quantitative IGH-PCR X. The method utilizes an international standardized approach as mentioned Rawstron AC, Fazi C, Agathangelidis A, et al. .

MRD values will be categorized into three different MRD levels: low ($<10^{-4}$, i.e. less than 1 CLL cell per 10,000 leukocytes), intermediate ($\geq 10^{-4}$ and $<10^{-2}$) and high ($\geq 10^{-2}$). MRD negativity is defined as $<10^{-4}$ and patients are defined as MRD negative if their disease burden is below this threshold at one executive timepoint.

MRD assessments of peripheral blood are to be performed at screening (for baseline characterization of the individual CLL clone). Further MRD assessments are to be performed:

- PB after cycle 2, 9, 12, at day 15 of cycle 15 and at month 27 for all patients;
- Every 3 months for 2 years and every 4 months for the 3rd year after cycle 15 for patients achieving MRD negativity
 - Patients becoming MRD pos. retest 1 month later
 - Bone marrow at day 15 of cycle 15 and at month 27

For assessment of MRD, a first pull sample is needed. The results of the MRD measurements will be sent to the local investigator **within 1 week**.

Further details about MRD logistics can be found in the lab manual.

10.7 Central review

10.7.1 Cytological and immunophenotype review

The diagnosis is confirmed centrally according to IWCLL criteria and the minimal requirements for diagnosis of CLL established within the ERIC collaboration.

For the final analysis of the study, the local immunophenotyping can be compared to the central flowcytometry results at baseline that are a prerequisite for subsequent MRD measurements.

10.8 Side studies

The following biomarker / side studies will be performed. These studies will provide significant insight into the effect of both intraclonal diversity and tumor microenvironmental factors on therapeutic responses:

1. Next Generation Sequencing (NGS) will be performed at baseline and at progression for recurrent mutations in CLL in alignment with the pan-European effort by ERIC. Bioinformatics, NGS platforms and statistics pipelines are present at Amsterdam Medical Center and Copenhagen University Hospital.
2. Viable frozen primary CLL cells are collected at the indicated time points in central biobanks in Amsterdam and Copenhagen along with preparations for serum/plasma, DNA, RNA etc. for translational studies that will focus on aspects that reflect the (patho)biology of the primary CLL cells and microenvironment and provide means for further tailoring of CLL treatment.

Further details about the side studies can be found in the lab manual.

11 Withdrawal of patients or premature termination of the study

11.1 Withdrawal of individual patients from protocol treatment

Patients should be withdrawn from protocol treatment if any of the following criteria for withdrawal are met:

- ◆ Death

- ◆ Progressive disease after cycle 6 of induction treatment
In case of suspected progressive disease according to IWCLL at or after start of cycle 6, response assessment will be performed and only patients with at least SD will continue on trial; patients with progressive disease will go off protocol treatment.
In the case of signs of progression before start of cycle 6 i.e. Richter's, the local investigator must make a full diagnostic work up to assess whether the patient should go off protocol treatment due to progression.
- ◆ Progressive disease after at least 3 cycles of reinitiation treatment
- ◆ If, for whatever reason, one or both drugs are not given for more than 56 consecutive days
- ◆ If the patient receives systemic treatment for another malignancy during the protocol treatment

Patients can leave the study at any time for any reason if they wish to do so without any consequences. The investigator can also decide to withdraw a patient from protocol treatment for other reasons than the criteria described above. Examples of such reasons for withdrawal from protocol treatment are:

- ◆ Excessive toxicity
- ◆ Refusal of patient to continue protocol treatment
- ◆ No compliance of the patient: patient is unable or unwilling to adhere to the treatment schedule and/or procedures required by the protocol

Patients who are withdrawn from protocol treatment will receive medical care according to local practice.

11.2 Follow up of patients withdrawn from protocol treatment

Patients who are withdrawn from treatment for other reasons than death will be followed as described in section 10.2 for follow up. SAE information will be collected as described in section 12.3.

However, for patients who are withdrawn from treatment because in hindsight they did not fulfill the eligibility criteria (see section 8.1) at time of enrolment, data will be collected until 30 days after the last protocol treatment given. SAE information will be collected as described in section 12.3

11.3 Withdrawal of informed consent

If a patient states he or she withdraws their consent to participate in the trial, the investigator should attempt to verify the patient's intent and record this in the patient's medical file:

- The patient can refuse further treatment and/or procedures according to protocol, while still consenting with further follow up data collection.
- The patient can refuse further treatment and/or procedures according to protocol, and withdraw consent for further follow up data collection.
- The patient can refuse further treatment and procedures according to protocol, withdraw consent for further follow up data collection and withdraw consent to use any data in the trial.

If the patient's intent is to withdraw consent for further data collection or to withdraw consent to use his or her data in the trial, the investigator should inform the HOVON Data Center so appropriate actions can be taken.

If the patient's intent cannot be verified, further follow up data will be collected for this patient as described in 10.2 for follow up.

11.4 Premature termination of the study

The sponsor may decide to terminate the study prematurely based on the following criteria:

- ◆ There is evidence of an unacceptable risk for study patients (i.e. safety issue);
- ◆ There is reason to conclude that continuation of the study cannot serve a scientific purpose following confirmation of the DSMB.
- ◆ The DSMB recommends to end the trial based on viable arguments other than described above.

The sponsor will promptly notify all concerned investigators, the Ethics Committee(s) and the regulatory authorities of the decision to terminate the study. The sponsor will provide information regarding the time lines of study termination and instructions regarding treatment and data collection of enrolled patients.

12 Safety

12.1 Definitions

Adverse event (AE)

An adverse event (AE) is any untoward medical occurrence in a patient or clinical study subject administered a medicinal product and which does not necessarily have a causal relationship with the treatment.

An AE can therefore be any unfavorable and unintended sign (including an abnormal laboratory finding), symptom, or disease temporally associated with the use of a medicinal (investigational) product, whether or not related to the medicinal (investigational) product.

Adverse event of special interest (AESI)

Atrial fibrillation and bleeding events are adverse events of special interest in this trial, and will be actively requested for.

Serious adverse event (SAE)

A serious adverse event is defined as any untoward medical occurrence or effect that at any dose:

- ◆ Results in death
- ◆ Is a life-threatening event (i.e. the patient was at immediate risk of death at the time the reaction was observed)
- ◆ Requires hospitalization or prolongation of an existing hospitalization
- ◆ Results in significant or persistent disability or incapacity
- ◆ Is a congenital anomaly or birth defect
- ◆ Is an *important medical event* (i.e. important adverse events that are not immediately life threatening or do not result in death or hospitalization but may jeopardize the patient or may require intervention to prevent one of the above characteristics/consequences, including suspected transmission of infectious agents by a medicinal product).

Note: TLS is *an important medical event* in this trial which must be reported as SAE.

Suspected unexpected serious adverse reaction (SUSAR)

All **suspected** Adverse Reactions which occur in the trial and that are both **unexpected** and **serious**.

Suspected adverse reactions (AR) are those AEs of which a reasonable causal relationship to any dose administered of the investigational medicinal product and the event is suspected. Unexpected adverse reactions are adverse reactions, of which the nature, or severity, is not consistent with the applicable product information (e.g. Investigator's Brochure for an unapproved IMP or Summary of Product Characteristics (SPC) for an authorized medicinal product).

12.2 Adverse event

12.2.1 Reporting of adverse events

Adverse events will be reported from the first study-related procedure until 30 days following the last dose of any drug from the protocol treatment schedule or until the start of subsequent systemic therapy for the disease under study, if earlier.

Adverse events occurring after 30 days should also be reported if considered at least possibly related to the investigational medicinal product by the investigator.

Adverse events have to be reported on the Adverse Events CRF. Adverse events will be scored according to the NCI Common Terminology Criteria for Adverse Events (CTCAE), version 4.0 (see appendix D).

Pre-existing conditions will be collected on the baseline concomitant diseases CRF, i.e. active (symptomatic) diseases of CTCAE grade ≥ 2 diseases under treatment, chronic diseases and long term effects of past events as present at the time of baseline assessment.

All adverse events have to be reported, **with the exception of:**

- ◆ A pre-existing condition that does not increase in severity; the pre-existing condition should be reported on the baseline concomitant diseases CRF
- ◆ AE's of CTCAE grade 1
- ◆ Abnormal laboratory values that have been recorded as being not clinically significant by the investigator in the source documents
- ◆ Relapse/Progression of the disease under study; complications as a result of disease progression remain reportable adverse events.

AESI must be filled out on a separate CRF.

12.2.2 Follow up of adverse events

All adverse events will be followed clinically until they have been resolved, or until a stable situation has been reached. Depending on the event, follow up may require additional tests or medical procedures as indicated, and/or referral to the general physician or a medical specialist.

On the AE CRF only the incidence of adverse events is recorded. Any ongoing adverse event that increases in severity is to be reported as a new adverse event on the CRF. Other follow up information is not collected on the CRF.

12.3 Serious Adverse Events

12.3.1 Reporting of serious adverse events

Serious Adverse Events (SAEs) will be reported from the first study-related procedure until 30 days following the last dose of any drug from the protocol treatment schedule or until the start of subsequent systemic therapy for the disease under study, if earlier.

Serious adverse events occurring after 30 days should also be reported if considered at least possibly related to the investigational medicinal product by the investigator.

All cases of TLS must be reported as SAE.

SAEs must be reported to the HOVON Data Center by e-mail **within 24 hours** after the event was known to the investigator, using the SAE report form provided. This initial report should contain a minimum amount of information regarding the event, associated treatment and patient identification, as described in the detail in the instructions for the SAE report form. Complete detailed information should be provided in a follow-up report within a further 2 business days, if necessary.

The following events do not require to be reported as a serious adverse event:

- ◆ Relapse/Progression of the disease under study; **death or complications as a result of disease progression remain reportable serious adverse events**
- ◆ Hospitalization for protocol therapy administration. Hospitalization or prolonged hospitalization for a complication of therapy administration will be reported as a serious adverse event.
- ◆ Hospitalization for diagnostic investigations (e.g., scans, endoscopy, sampling for laboratory tests, bone marrow sampling) that are not related to an adverse event. Hospitalization or prolonged hospitalization for a complication of such procedures remains a reportable serious adverse event.
- ◆ Prolonged hospitalization for technical, practical, or social reasons, in absence of an adverse event.
- ◆ Hospitalization for a procedure that was planned prior to study participation (i.e. prior to registration or randomization). This should be recorded in the source documents. Prolonged hospitalization for a complication of such procedures remains a reportable serious adverse event.

12.3.2 Causality assessment of Serious Adverse Events

The investigator will decide whether the serious adverse event is related to trial medication, i.e. any of the products from the protocol treatment schedule. The decision will be recorded on the serious adverse event report. The assessment of causality is made by the investigator using the following:

RELATIONSHIP	DESCRIPTION
UNRELATED	There is no evidence of any causal relationship
UNLIKELY	There is little evidence to suggest there is a causal relationship (e.g. the event did not occur within a reasonable time after administration of the trial medication). There is another reasonable explanation for the event (e.g. the patient's clinical condition, other concomitant treatments).
POSSIBLE	There is some evidence to suggest a causal relationship (e.g. because the event occurs within a reasonable time after administration of the trial medication). However, the influence of other factors may have contributed to the event (e.g. the patient's clinical condition, other concomitant treatments).
PROBABLE	There is evidence to suggest a causal relationship and the influence of other factors is unlikely.
DEFINITELY	There is clear evidence to suggest a causal relationship and other possible contributing factors can be ruled out.
NOT ASSESSABLE	There is insufficient or incomplete evidence to make a clinical judgment of the causal relationship.

12.3.3 Follow up of Serious Adverse Events

All serious adverse events will be followed clinically until they are resolved or until a stable situation has been reached. Depending on the event, follow up may require additional tests or medical procedures as indicated, and/or referral to the general physician or a medical specialist.

Follow up information on SAE's should be reported monthly until recovery or until a stable situation has been reached. The final outcome of the SAE should be reported on a final SAE report.

12.3.4 Processing of serious adverse event reports

The HOVON Data Center will forward all SAE reports within 24 hours of receipt to the Principal Investigator, and the manufacturer of the investigational medicinal product(s).

The HDC safety desk will evaluate if the SAE qualifies as a suspected unexpected serious adverse reaction (SUSAR).

The Investigators Brochure will be used as a reference document for expectedness assessment.

Where reporting of SAE's to the Ethics Committee is required by national laws or regulations or by the procedures of the Ethics Committee, the HOVON Data Center will report those SAE's by means of a six-monthly SAE line listing.

12.4 Reporting Suspected Unexpected Serious Adverse Reactions

The HDC Safety Desk, on behalf of the sponsor, will ensure the reporting of any SUSARs to the Ethics Committees (EC), the Competent Authorities (CA), the manufacturer of the IMP and the investigators in compliance with applicable laws and regulations, and in accordance with any trial specific agreements between the sponsor and a co-sponsor or the manufacturer of the IMP.

Expedited reporting of SUSARs will occur no later than 15 days after the HOVON Data Center had first knowledge of the serious adverse event. For fatal or life-threatening cases this will be no later than 7 days for a preliminary report, with another 8 days for a complete report.

The manner of SUSAR reporting will be in compliance with the procedures of the Ethics Committees and Health Authorities involved.

12.5 Pregnancies

Pregnancies of a female subject or the female partner of a male subject, occurring while the subject is on protocol treatment or within 30 days following the last dose of any drug from the protocol treatment schedule, should be reported to the sponsor. Pregnancies must be reported to the HOVON Data Center by e-mail within 24 hours after the event was known to the investigator, using the pregnancy report form provided.

The investigator will follow the female subject until completion of the pregnancy, and must notify the sponsor of the outcome of the pregnancy within 5 days or as specified below. The investigator will provide this information as a follow-up to the initial pregnancy report. If the outcome of the pregnancy meets the criteria for classification as a SAE (i.e., spontaneous or therapeutic abortion, stillbirth, neonatal death, or congenital anomaly - including that in an aborted fetus), the investigator should follow the procedures for reporting SAEs. In the case of a live "normal" birth, the sponsor should be informed as soon as the information is available. All neonatal deaths that occur within 30 days of birth should be reported, without regard to causality, as SAEs. In addition, any infant death after 30 days that the investigator suspects is related to the *in utero* exposure to the investigational medicinal product(s) should also be reported.

The investigator is encouraged to provide outcome information of the pregnancy of the female partner of a male subject, if this information is available to the investigator and the female partner gives her permission.

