8.1.1 Inclusion criteria

- ◆ Documented relapsed/refractory CLL or SLL requiring treatment according to IWCLL criteria (no limits on previous treatment lines; CD20 and steroids are not considered prior therapy lines).
- ◆ Age at least 18 years.
- ◆ Adequate bone marrow function defined as:
 - Absolute neutrophil count (ANC) $>0.75 \times 10^9/L$
 - Platelet count $>30,000 /\mu L$ $30 \times 10^9/L$.
 - Hemoglobin $>8.0 \text{ g/dL}$ (5 mmol/L)Unless directly attributable to CLL infiltration of the bone marrow, proven by bone marrow biopsy
- ◆ Creatinine clearance (CrCL) $\geq 30 \text{ ml/min}$ calculated according to the modified formula of Cockcroft and Gault or directly measured with 24hr urine collection.
- ◆ Adequate liver function as indicated
 - Serum aspartate transaminase (AST) or alanine transaminase (ALT) $\leq 3.0 \times$ upper limit of normal (ULN)
 - Bilirubin $\leq 1.5 \times$ ULN (unless bilirubin rise is due to Gilbert's syndrome or of non-hepatic origin)
 - Prothrombin time (PT)/International normal ratio (INR) $<1.5 \times$ ULN and PTT (activated partial thromboplastin time [aPTT]) $<1.5 \times$ ULN (unless abnormalities are related to coagulopathy or bleeding disorder).
- ◆ Negative serological testing for hepatitis B (HBsAg negative and anti-HBc negative; patients positive for anti-HBc may be included if PCR for HBV DNA is negative and HBV-DNA PCR is performed every month until 12 months after last dose), negative testing for hepatitis C RNA within 42 days prior to registration.
- ◆ WHO/ECOG performance status 0-3 (appendix C), stage 3 only if attributable to CLL.
- ◆ Negative pregnancy test at study entry (for women of childbearing potential).
- ◆ Male and female subjects of reproductive potential must agree to use both a highly effective method of birth control (e.g. implants, injectables, combined oral contraceptives, some

intrauterine devices [IUDs], complete abstinence , or sterilized partner) and a barrier method (e.g., condoms, cervical ring, sponge, etc.) during the period of therapy and for 90 days after the last dose of study drug.

- ◆ Ability and willingness to provide written informed consent and to adhere to the study visit schedule and other protocol requirements.
- ◆ Written informed consent.

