9.2.5 Embryo-Fetal Toxicity

Based on its mechanism of action and findings in animals, venetoclax may cause embryo-fetal harm when administered to a pregnant woman. In an embryo-fetal study conducted in mice, administration of venetoclax to pregnant animals at exposures equivalent to that observed in patients at the recommended dose of 400 mg daily resulted in post-implantation loss and decreased fetal weight. There are no adequate and well-controlled studies in pregnant woman using venetoclax. Advise females of reproductive potential to avoid pregnancy during treatment. If venetoclax is used during pregnancy or if the patient becomes pregnant while taking venetoclax, the patient should be apprised of the potential hazard to the fetus.

There are no adequate and well-controlled studies of ibrutinib in pregnant women. Based on findings in animals, ibrutinib may cause fetal harm when administered to pregnant women. Based on findings in animal trials, ibrutinib is teratogenic and may cause fetal harm such as postimplantation loss, increased visceral malformations, increased skeletal malformations or decreased fetal weights. No teratogenicity events have been reported from the available clinical trials. Therefore ibrutinib should not be used during pregnancy. Women of child-bearing potential must use highly effective contraceptive measures while taking ibrutinib. Those using hormonal methods of birth control must add a second barrier method. Women should avoid becoming pregnant while taking ibrutinib and for up to 3 months after ending treatment. If this drug is used during pregnancy or if the patient becomes pregnant while taking this drug, the patient should be apprised of the potential hazard to a fetus. The time period following treatment with ibrutinib when it is safe to become pregnant is unknown.

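### Pregnancy reporting stops 30 days after the last dose, while the protocol's own contraception period runs to 90 days

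*Protocol*

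**What the plan says.** Three sections of the protocol set a time limit that bears on pregnancy after treatment.

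- **Section 12.5 (Pregnancies)** sets the reporting duty. It applies to female patients and to the partners of male patients, for as long as the patient is being treated. Once treatment has ended, the limit is that pregnancies "within 30 days following the last dose of any drug from the protocol treatment schedule, should be reported to the sponsor". The report is due within 24 hours of the investigator learning of the pregnancy. A female patient is then followed until the pregnancy ends. For the partner of a male patient, the investigator is only encouraged to supply the outcome, and only with her permission.
- **Section 8.1.1 (Inclusion criteria)** sets the contraception duty. Male and female patients of reproductive potential must use it "during the period of therapy and for 90 days after the last dose of study drug".
- **Section 9.2.5 (Embryo-Fetal Toxicity)** gives the advice for ibrutinib: "Women should avoid becoming pregnant while taking ibrutinib and for up to 3 months after ending treatment". It adds: "The time period following treatment with ibrutinib when it is safe to become pregnant is unknown". For venetoclax it advises avoiding pregnancy during treatment and gives no interval afterwards.

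Two further provisions could catch part of what section 12.5 leaves out. Section 12.3.1 keeps a route open that depends on causality: "Serious adverse events occurring after 30 days should also be reported if considered at least possibly related". Section 12.1 lists this among the criteria for a serious event: "Is a congenital anomaly or birth defect".

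**The concern.** The protocol asks patients to prevent pregnancy for three times as long after the last dose as it asks investigators to report one. If prevention fails in the second or third month, the sponsor need not be told, although the protocol thought the period important enough to require contraception throughout it.

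What is at stake is the completeness of pregnancy safety data for two drugs that section 9.2.5 says may harm a fetus, at a time after treatment when the protocol admits that it does not know whether pregnancy is safe. Such data are useful only if every pregnancy is counted, including those that end normally. If only adverse outcomes that someone attributes to the drug are collected, there is no denominator, and the collection depends on a causality judgement.

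The design makes the interval relevant. Arm B patients stop both drugs after cycle 15 and stay under study follow-up without treatment (sections 9.3 and 10.1). Patients withdrawn from treatment are also followed (section 11.2). Sites will therefore be in contact with patients who are off drug and still within the 90 days.

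**Working it through.** No error rate or sample-size formula applies, and the plan gives no figure to reproduce. The check sets the stated windows side by side, counted from the last dose.

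| Rule | Section | Who is covered | Length after last dose |
|---|---|---|---|
| Report the pregnancy | 12.5 | Female patients; partners of male patients | 30 days |
| Use contraception | 8.1.1 | Male and female patients of reproductive potential | 90 days |
| Avoid pregnancy (ibrutinib) | 9.2.5 | Women | Up to 3 months |

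**Step 1: length of the gap.** Contraception window minus reporting window = 90 − 30 = 60 days, that is, days 31 to 90.

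**Step 2: share of the precautionary period.** 60 / 90 = 0.67, so 67% of it has no pregnancy-reporting duty. This is a share of calendar days. It is not a share of expected pregnancies, because the protocol does not say how many patients are of reproductive potential or how many pregnancies it expects.

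**Step 3: does another rule close the gap?**

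- *Late serious adverse events (section 12.3.1).* These remain reportable after 30 days, but only if the investigator considers them at least possibly related. A congenital anomaly counts as serious under section 12.1, so it could be reported this way. Pregnancy as such is not among the criteria in section 12.1.
- *Outcome rules within section 12.5.* Abortion, stillbirth, neonatal death and congenital anomaly go through the serious adverse event procedures. Neonatal deaths within 30 days of birth are reportable whatever the cause, and later infant deaths if related exposure in utero is suspected. These sentences stand within the follow-up of a pregnancy already reported. Even if they are read as applying to any pregnancy, the site must first learn of the outcome, and without follow-up of the pregnancy it may not.
- *Other sections.* None lengthens the pregnancy window. The 30 days match the general windows for adverse events (section 12.2.1) and serious adverse events (section 12.3.1). The protocol does depart from that limit elsewhere: section 12.6 collects second primary malignancies until 5 years after registration, regardless of cause.

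**Step 4: what remains uncovered on days 31 to 90.** There is no duty to notify the pregnancy, for a patient or for a partner. For a female patient there is no duty to follow it to outcome. Normal outcomes are not captured. Outcomes judged unrelated are not captured either, unless the neonatal-death sentence is read as standing alone.

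**Step 5: when a site would meet such a case.** Visits after cycle 15 are every 3 months (section 10.1). For an arm B patient the first of these falls at about the end of the 90 days. A pregnancy that began on days 31 to 90 may come to light then, with no instruction to report it.

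**The case against.** The strongest reply is that nothing here is inconsistent. Section 8.1.1 binds patients and section 12.5 binds investigators, and both can be obeyed at once. Section 12.5 simply applies the protocol's general 30-day limit. This stands: the windows are misaligned, and a reader who infers that they contradict each other goes beyond the text.

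Four other inferences are tempting and are not supported.

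- *That section 9.2.5 warns of fetal harm for 3 months after treatment.* Its statements on harm concern use during pregnancy. The 3 months are advice to avoid conceiving after ibrutinib, and the safe interval is said to be unknown. Days 31 to 90 are therefore a precautionary period. The protocol gives no elimination data that would show a conception in that interval to be an exposed one.
- *That every such case is lost.* Serious outcomes judged at least possibly related stay reportable. The loss is of routine notification and follow-up, and of the outcomes that the causality filter removes.
- *That a longer window would secure outcome data for partners.* Partner outcomes are only encouraged even within 30 days. For partners, a longer window adds notification and nothing firmer. The 90 days for men also rest on section 8.1.1 alone.
- *That all of arm B is affected.* Only patients of reproductive potential, or with such partners, are concerned.

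It can also be argued that arm B observation counts as being on protocol treatment, since section 14.1 calls it one of two maintenance treatment arms. The text does not settle this, but section 9.3 describes the arm as treatment free, which favours the opposite reading. Even on the generous reading, the gap remains for patients who discontinue treatment.

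**Conclusion.** The concern holds as a misalignment in safety reporting. Sixty of the 90 days for which the protocol asks patients to prevent pregnancy carry no duty to report one or, in a female patient, to follow it to outcome. The late serious adverse event rule is a partial safety net: it depends on the site learning of the outcome and judging it possibly related.

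The practical size is small. Few pregnancies are to be expected in a trial of relapsed or refractory CLL, although that is an expectation and not a figure from the protocol. The primary endpoint and the sample size are unaffected. The conclusion assumes that an untreated arm B patient is not on protocol treatment; if that is wrong, the point is confined to patients who discontinue. It takes no view on how long contraception should last. The change is worth making because it costs very little and uses a figure the protocol already contains.

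**What to change.** Reconcile section 12.5 with sections 8.1.1 and 9.2.5. In section 12.5, make pregnancies reportable if they occur on protocol treatment or within the post-treatment contraception period stated in section 8.1.1, currently 90 days after the last dose. Make the same change in the pregnancy report form instructions. Leave the contraception rule itself as it is. Wording section 12.5 as a reference to section 8.1.1 would keep the two together if that period is ever amended.

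The cost is one number in the protocol, the matching form instructions and a few extra pregnancy reports. No analysis changes.
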